5.1.1 Method of Assigning Subjects to Treatments and Blinding

Subjects selected for participation will be randomly assigned to one of the two treatment arms, 264 subjects will be assigned to either treatment arm A (receiving EPIAO) or B (receiving EPREX) in a ratio of 1:1.

The randomization schedule will be generated by EA statistical team, using PROC PLAN in SAS, version 9.2 or higher, according to EA standard operating procedures (SOPs), listing subject randomization code number and treatment. The randomization allocation will be done by Interactive Voice Response System/ Interactive Web Response System (IVRS/IWRS) for dispensing the test drugs.

The investigator and sponsor's Medical and Safety Expert will have to contact the IVRS/IWRS for information regarding the identity of treatment sequence for each subject.

All subjects, who sign an IRB/IEC approved informed consent form and authorization for the use and disclosure of protected health information, will be assigned a unique subject identity code (SIC) consisting of two digit center code and three digit subject specific code. The randomization code will be captured separately as an additional identity.

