5.1.6 Blinding and Unblinding

This will be a double blinded and randomized study. All investigators, subjects, site personnel (except the study nurse performing the drug administration and pharmacist) and Contract Research Organization (CRO) study team [except persons involved in preparation of the codes, clinical operations team in Russia and project manager who is responsible for convening the Safety Monitoring Committee (SMC) meeting] will be blinded to the medication codes.

A treating physician may request unblinding of study medication on an individual subject, if it is essential for the clinical management of the subject's health, to ensure safety. If a treating physician requires unblinding of study medication for a subject, e.g. for management of a SAE, investigators will be able to access this information via IVRS/IWRS. The sponsor / EA medical monitor should be contacted immediately (preferably before unblinding takes place) and the date and reason for unblinding has to be documented in the source document (medical record) and CRF, accordingly. The EA medical monitor or designee is required to contact and inform the sponsor regarding unblinding of the subject's treatment.

Blinding process in Thailand:

Co-sponsor will be responsible for IP relabeling/redressing. In this step, randomization number & kit number of each patient will be generated by IWRS, and then same will be informed to the un-blinded co-sponsor. The un-blinded person will know which of the IP, either EPIAO or EPREX needs to be administrated to each patient according to IWRS. Consequently, un-blinded co-sponsor will prepare double-blind re-labelled IP accordingly and then all pre-labelled IP will be shipped to each site. The blinded nurses/or blinded study coordinator will take the IP to un-blinded nurse to make injections to blinded patients.

Blinding process in Russia:

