At each site, an un-blinded person (pharmacist) will be responsible for IP relabeling/redressing. In this step, randomization number & IP name of each patient will be generated by IWRS, and then same will be informed to the un-blinded person (study nurse/pharmacist). The un-blinded person will know which of the IP, either EPIAO or EPREX needs to be administrated to each patient according to IWRS. Consequently, un-blinded person (study nurse/pharmacist) will prepare double-blind re-labelled IP. The un-blinded nurse will take IP from un-blinded person (study nurse/pharmacist) to make injections to blinded patients. Investigator who will perform routine assessment of the patient will be blinded.

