Treatment period:

The dose should be adjusted for each patient to achieve and maintain hemoglobin levels between 10-12 g/dl. The maximum dose of study drug is 300 IU/kg.

[figure not shown]
The investigator can adjust the dose by their own decision based on the best interest and safety of the subject and in any time

Two key factors will be considered for dose adjustment during the study period

1. Hemoglobin level at current visit
2. Changes in hemoglobin over past 4 weeks

- If haemoglobin decreases more than 1 g/dl over the past 4 weeks and current haemoglobin level is < 10.5 g/dl, the dosage may be raised by 25% of the last dose received by the subject (A).
- If haemoglobin decreases more than 1 g/dl over the past 4 weeks and current haemoglobin level is between 10.5 g/dl to 12.0 g/dl, the last dose received by the subject should be continued (B).
- If haemoglobin decreases more than 1 g/dl over the past 4 weeks but current haemoglobin is between 12.1 to 13.0 g/dl, the dose should be reduced by 25% of the last dose received by the subject (C).
- If haemoglobin decreases or an increase between 1.0 g/dl and current haemoglobin value is less than 10.5 g/dl, the dosage may be raised by 25% of the last dose received by the subject (D).
- If haemoglobin decreases or an increase between 1.0 g/dl and the current hemoglobin value is between 10.5 to 12.0 g/dl, the last dose received by the subject should be continued (E).
- If haemoglobin decreases or increase between 1.0 g/dl but the current haemoglobin is between 12.1 to 13.0 g/dl, the dose should be reduced by 25% of the last dose received by the subject (F).
- If haemoglobin increases more than 1 g/dl over the past 4 weeks and current haemoglobin is < 10.5 g/dl, the last dose received by the subject should be continued (G).
- If haemoglobin increases more than 1 g/dl over the past 4 weeks and haemoglobin level is between 10.5 to 12.0 g/dl, the last dose received by the subject should be continued (H).
- If haemoglobin increases more than 1 g/dl over the past 4 weeks but current haemoglobin is between 12.1 to 13.0 g/dl, the dose should be reduced by 25% of the last dose received by the subject (I).
- If current haemoglobin level is greater than 13.0 g/dl, not depending on the change of haemoglobin in the past 4 weeks, dose should be temporarily withheld until the haemoglobin begins to decrease between 10.5 and 12.0 g/dl, at which point therapy should be reinitiated at 25% reduced from the previous dose (J).

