7 EFFICACY ASSESSMENTS

The efficacy variables which will be assessed in this study are as follows:

- Mean absolute change in haemoglobin level (g/dl) in subjects before and after 6-months of treatment with EPIAO/EPREX
- Mean absolute change in weekly epoetin dosage per kg body weight (IU/kg/week) before and after 6-month treatment with EPIAO/EPREX.
- Proportion of subjects with any haemoglobin measurement outside the target range during the double-blind treatment period
- Incidence of blood transfusions

The haemoglobin assessment will be performed at all the scheduled visits and the epoetin dosage required for each subject will be calculated by the investigator and the same will be documented in the Electronic Case Report Form (eCRF).

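### Section 5.1.1 has the investigator look up each subject's treatment identity in IVRS/IWRS, contradicting the investigator blinding in section 5.1.6

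*Protocol*

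**What the plan says.** Section 5.1.1 describes how the randomisation list is generated and says that IVRS/IWRS performs the allocation for dispensing. It then says that the investigator and the sponsor's Medical and Safety Expert "will have to contact the IVRS/IWRS for information regarding the identity of treatment sequence for each subject".

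Section 5.1.6 sets the blind. Those kept blind to the medication codes begin with "All investigators, subjects, site personnel (except the study nurse performing the drug administration and pharmacist"), and the list continues with the CRO team apart from named exceptions. The route to a code is narrow: "A treating physician may request unblinding of study medication on an individual subject". The condition attached to such a request is that it may be made only "if it is essential for the clinical management of the subject's health, to ensure safety". The medical monitor is to be contacted, preferably beforehand, and the date and reason recorded.

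The same section says who learns the product:

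- **Thailand:** the un-blinded co-sponsor is given the IWRS output, relabels the product and ships it to the sites.
- **Russia:** "randomization number & IP name of each patient will be generated by IWRS", and this is passed to the un-blinded study nurse or pharmacist. The text adds: "Investigator who will perform routine assessment of the patient will be blinded".

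On dose, section 7 says that "the epoetin dosage required for each subject will be calculated by the investigator". Section 5.1.7 says: "The investigator can adjust the dose by their own decision based on the best interest and safety of the subject and in any time". It also describes its adjustment rules as advisory.

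**The concern.** The sentence in 5.1.1 is mandatory, covers every subject and carries no emergency condition. It directly follows the sentence on allocation, so it reads as a routine step. What it asks for is treatment identity, not a randomisation or kit number. An investigator who complied would know the arm of each subject.

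That would be damaging in most double-blind trials and is more so here. Change in weekly epoetin dose per kg is a primary endpoint (section 3.1.3), called co-primary in section 9.8, and it is the direct product of the investigator's decisions. Haemoglobin, the other co-primary endpoint, responds to dose. The investigator also judges adverse event causality (section 8.1.1.4). In an equivalence trial, an investigator who knows the arm could hold doses steady in line with the expected 1:1 conversion, which would make the arms look alike, or could adjust more readily in one arm. The protocol's own rationale (section 1.2) cites the guideline minimum that whoever decides on dose adjustment be masked to allocation.

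**Working it through.** No stated figure in the protocol bears on this point, so there is none to reproduce. The check sets the sections side by side.

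| Question | Section 5.1.1 | Section 5.1.6 |
|---|---|---|
| Does the investigator learn treatment identity? | Yes, from IVRS/IWRS | No, investigators are blinded |
| For whom? | Each subject | An individual subject |
| Under what condition? | None stated | Clinically essential, for safety |
| Safeguards? | None stated | Medical monitor contacted; date and reason documented |
| Who receives identity routinely? | Investigator and the sponsor's Medical and Safety Expert | Co-sponsor (Thailand); study nurse or pharmacist (Russia) |

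The entries conflict on every row.

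For the sponsor's Medical and Safety Expert the contradiction is less explicit, because the blinding sentence in 5.1.6 lists investigators, subjects, site personnel and the CRO team, not sponsor staff. However, 5.1.6 does not name this role among those who receive identity, and section 9.6 sends the interim results to an independent sponsor representative and keeps all other study personnel blinded.

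**Link to the endpoint.** The investigator calculates the dose (section 7), may change it at any time (section 5.1.7), and the resulting change in dose per kg is compared with ±45 IU/kg/week (section 9.4.1).

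**Scale of one dose decision.** Inputs: a step of 2000 IU per week (section 5.1.7), body weights of 58 and 75 kg (the stratum cut-points in section 9.8), and the margin of 45 IU/kg/week. Section 5.1.7 also describes percentage changes; 2000 IU is used here only as a yardstick, and no view is taken on which rule governs.

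- At 58 kg: 2000 / 58 = 34.5 IU/kg/week; 34.5 / 45 = 77% of the margin.
- At 75 kg: 2000 / 75 = 26.7 IU/kg/week; 26.7 / 45 = 59% of the margin.

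These are shifts for one subject. The shift in an arm's mean is f × 2000 / weight, where f is the fraction of that arm given one extra step because the arm is known. The protocol gives no value for f, so the values below are assumptions:

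| Assumed f | Mean shift, 75 to 58 kg (IU/kg/week) | Share of the ±45 margin |
|---|---|---|
| 5% | 1.3 to 1.7 | 3% to 4% |
| 10% | 2.7 to 3.4 | 6% to 8% |
| 20% | 5.3 to 6.9 | 12% to 15% |

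**The case against.** The strongest reply is that the sentence says only where the codes are held: anyone who needs a subject's treatment must go through IVRS/IWRS. Pairing the investigator with the sponsor's Medical and Safety Expert, who has no allocation or dispensing role, suits a code-break route. Sections 5.1.6 and 8.3.1 both describe investigator access through IVRS/IWRS in an emergency or for a serious adverse event. On this view 5.1.6 is the specific section, already protects the blind, and governs.

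Part of this stands. Section 5.1.6 makes it clear that investigators were meant to be blinded. The intended meaning of 5.1.1 may well be the emergency route, or fetching a number. But the sentence says neither, and the protocol has other words for both: it states emergency conditions where it means them, and refers to randomisation and kit numbers in the Thai process. The reference to a treatment sequence does not fit a parallel-group trial either. Nothing in the document says which section prevails.

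Three stronger readings are tempting but unsupported:

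- **That the trial was designed with an unblinded investigator.** Section 5.1.6 says the reverse, twice.
- **That Russian investigators would see the product name because IWRS generates it there.** The same sentence sends that output to the un-blinded nurse or pharmacist, and nothing says that an investigator's login displays it.
- **That the equivalence conclusion is threatened by a known amount.** The mean shifts above rest on assumed fractions, and even at 20% they stay at or below about 15% of the margin.

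**Conclusion.** The contradiction is real and should be corrected. As written, 5.1.1 instructs a routine disclosure of treatment identity that 5.1.6 forbids, and it does so for all 264 subjects and for the person whose decisions generate a co-primary endpoint. It is an inconsistency in the text, not a flawed design choice.

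The conclusion rests on the plain wording of the two sections and on the investigator's documented control of dose. It does not depend on any assumed bias. The effect on the group mean dose cannot be estimated from the protocol. Whether any blind would be broken in practice depends on how IWRS access is configured, which the protocol does not show.

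**What to change.** Reword the sentence in 5.1.1 along these lines: the investigator and the sponsor's Medical and Safety Expert use IVRS/IWRS only to randomise, and receive no treatment identity, only the randomisation number and, where used, the kit number. Treatment identity is released only to the un-blinded persons named in 5.1.6 for each country (the co-sponsor in Thailand, the study nurse or pharmacist in Russia), and to anyone else only through the unblinding procedure in 5.1.6.

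The wording must keep the Thai co-sponsor as a recipient. It should not presume a kit number in Russia, where 5.1.6 describes only a randomisation number and product name. Drop the word sequence.

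Then confirm that the IWRS user roles match the revised text. The cost is one sentence and a check of access rights; no dose rule, visit or analysis changes.

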5.1.2 Method of Assessing Treatment Compliance

Subjects will be asked about their compliance at each visit. This information will be appropriately recorded at scheduled visit in the CRF. Subjects judged to be non-compliant will be counselled on the importance of one to three times weekly administration of study medication, as prescribed. Subjects who are repeatedly or severely non-compliant may be discontinued, at investigator's discretion after discussion with the medical monitor.

5.1.3 Labeling and Packaging

It will be the sponsor's responsibility to provide the trial products. Packaging and labelling will be done as per local regulatory regulations and trial requirements.

The following general information will be provided on the clinical trial supply label:

- Product name – Study Number
- Subject #, subject initials
- Brief Instructions for use
- Storage Instructions
- Cautionary Statement – “For clinical trial purpose only”
- Batch or Lot #
- Date dispensed
- Expiry date
- Supplier of drug

5.1.3.1 Preparation

The dose of erythropoietin will be calculated based on the haemoglobin level. The study medication will be supplied in the form of pre-filled syringes for administration.

5.1.4 Storage

The study treatment supplies should be stored in a secure location and maintained at a temperature of 2°C to 8°C (refrigerated temperature). The pre-filled syringes should be protected from light.

5.1.5 Drug Accountability

When a drug shipment is received, unblinded pharmacist will check the amount and condition of the drug, temperature log during the transit, check for appropriate local language in the label, drug expiration date, and sign the Receipt of Shipment Form provided. The original will be retained at the site. In addition, the unblinded pharmacist shall contact Sponsor or Sponsor representative (local depot) as soon as possible if there is a problem with the shipment. The unblinded pharmacist will be responsible for blinding of IMP after receipt of the drug shipment.

The investigator designated person who is un-blinded, preferably a pharmacist, will be responsible for drug accountability, reconciliation, and record maintenance. In accordance with all applicable regulatory requirements, the designated site staff (study pharmacist) will maintain accurate IP accountability records throughout the course of the study. A drug accountability log for recording the receipt, dispensing and return of drug will be maintained to document the amount of drug received and the amount of drug used in the study. Study medication requests, receipts and dispensing records as well as study medication inventory forms will be examined and reconciled during and at the end of the study by EA personnel.

All unused or partially used study drug must be returned to sponsor or its representatives at the end of the study for destruction. Reconciliation between the amounts of drug supplied, used and

returned to EA must be performed and any discrepancies should be accounted for. This reconciliation will be logged on the drug reconciliation form, signed and dated. The study drug destroyed on site will be documented in the study files.

A Drug Accountability Record will be provided for the drugs. The record must be kept current and should contain, the date and quantities of drug received, subject's identification number and/or initials or supply number as applicable, for whom the IP was dispensed, the date and quantity of IP dispensed and the remaining IP.

5.1.6 Blinding and Unblinding

This will be a double blinded and randomized study. All investigators, subjects, site personnel (except the study nurse performing the drug administration and pharmacist) and Contract Research Organization (CRO) study team [except persons involved in preparation of the codes, clinical operations team in Russia and project manager who is responsible for convening the Safety Monitoring Committee (SMC) meeting] will be blinded to the medication codes.

A treating physician may request unblinding of study medication on an individual subject, if it is essential for the clinical management of the subject's health, to ensure safety. If a treating physician requires unblinding of study medication for a subject, e.g. for management of a SAE, investigators will be able to access this information via IVRS/IWRS. The sponsor / EA medical monitor should be contacted immediately (preferably before unblinding takes place) and the date and reason for unblinding has to be documented in the source document (medical record) and CRF, accordingly. The EA medical monitor or designee is required to contact and inform the sponsor regarding unblinding of the subject's treatment.

Blinding process in Thailand:

Co-sponsor will be responsible for IP relabeling/redressing. In this step, randomization number & kit number of each patient will be generated by IWRS, and then same will be informed to the un-blinded co-sponsor. The un-blinded person will know which of the IP, either EPIAO or EPREX needs to be administrated to each patient according to IWRS. Consequently, un-blinded co-sponsor will prepare double-blind re-labelled IP accordingly and then all pre-labelled IP will be shipped to each site. The blinded nurses/or blinded study coordinator will take the IP to un-blinded nurse to make injections to blinded patients.

Blinding process in Russia:

At each site, an un-blinded person (pharmacist) will be responsible for IP relabeling/redressing. In this step, randomization number & IP name of each patient will be generated by IWRS, and then same will be informed to the un-blinded person (study nurse/pharmacist). The un-blinded person will know which of the IP, either EPIAO or EPREX needs to be administrated to each patient according to IWRS. Consequently, un-blinded person (study nurse/pharmacist) will prepare double-blind re-labelled IP. The un-blinded nurse will take IP from un-blinded person (study nurse/pharmacist) to make injections to blinded patients. Investigator who will perform routine assessment of the patient will be blinded.

5.1.7 Dosing Schedule, Selection and Timing of dosing

Study drugs have to be administered in strict accordance with approved protocol.

Treatment arm A

EPIAO group (test product) having 132 subjects will receive EPIAO, one to three times a week, intravenously for period of 52 weeks at the end of dialysis session

Treatment arm B

EPREX group (reference product) having 132 subjects will receive EPREX, one to three times a week, intravenously for period of 52 weeks at the end of dialysis session

The blood pressure will be monitored after the haemodialysis procedure and if the blood pressure is within the normal range then the study medication will be administrated by the study nurse or designee. If systolic pressure >160 mm of Hg, the blood pressure will be monitored after half an hour. If the BP does not decrease then the subject will be asked to come the next day for drug administration.

The dose will be adjusted individually to maintain haemoglobin at a level not exceeding 12 g/dl. The required dose will be calculated based on the haemoglobin.

Dosage adjustment:

Titration period:

During titration period, EPREX will be administered one to three times weekly as per last dose which subject received previously before screening, for subject who are already on treatment. EPREX will be administered one to three times weekly as per Hb value at screening and as per PI discretion. The dose received by the subject at screening will be taken as the "basic initial dose" for all subjects. An increase or decrease of 2000 IU per week will be allowed for dose adjustment to maintain subject's Hb value within target range (10 – 12.5 g/dl). At this point, the "stable dose" of EPREX for each patient will be determined. The stable dose of EPREX / EPIAO will be calculated as IU/kg/week before the start of the treatment period and captured in the eCRF. In substantiated cases, a prolongation of the titration period is allowed up to maximum of 4 to 5 months on a case to case basis which will be considered as extended titration period.

During treatment period, subjects randomized to EPREX arm will continue on an equivalent dose of EPREX as during the titration period. Subjects randomized to EPIAO arm will receive EPIAO treatment 1:1 dose conversed from that of EPREX during the titration period. If subject's Hb value is out of target range, an increase or decrease of 2000 IU per week is allowed for dose adjustment. The maximum allowable dose is 300 IU/kg/week.

Treatment period:

The dose should be adjusted for each patient to achieve and maintain hemoglobin levels between 10-12 g/dl. The maximum dose of study drug is 300 IU/kg.

[figure not shown]
The investigator can adjust the dose by their own decision based on the best interest and safety of the subject and in any time

Two key factors will be considered for dose adjustment during the study period

1. Hemoglobin level at current visit
2. Changes in hemoglobin over past 4 weeks

- If haemoglobin decreases more than 1 g/dl over the past 4 weeks and current haemoglobin level is < 10.5 g/dl, the dosage may be raised by 25% of the last dose received by the subject (A).
- If haemoglobin decreases more than 1 g/dl over the past 4 weeks and current haemoglobin level is between 10.5 g/dl to 12.0 g/dl, the last dose received by the subject should be continued (B).
- If haemoglobin decreases more than 1 g/dl over the past 4 weeks but current haemoglobin is between 12.1 to 13.0 g/dl, the dose should be reduced by 25% of the last dose received by the subject (C).
- If haemoglobin decreases or an increase between 1.0 g/dl and current haemoglobin value is less than 10.5 g/dl, the dosage may be raised by 25% of the last dose received by the subject (D).
- If haemoglobin decreases or an increase between 1.0 g/dl and the current hemoglobin value is between 10.5 to 12.0 g/dl, the last dose received by the subject should be continued (E).
- If haemoglobin decreases or increase between 1.0 g/dl but the current haemoglobin is between 12.1 to 13.0 g/dl, the dose should be reduced by 25% of the last dose received by the subject (F).
- If haemoglobin increases more than 1 g/dl over the past 4 weeks and current haemoglobin is < 10.5 g/dl, the last dose received by the subject should be continued (G).
- If haemoglobin increases more than 1 g/dl over the past 4 weeks and haemoglobin level is between 10.5 to 12.0 g/dl, the last dose received by the subject should be continued (H).
- If haemoglobin increases more than 1 g/dl over the past 4 weeks but current haemoglobin is between 12.1 to 13.0 g/dl, the dose should be reduced by 25% of the last dose received by the subject (I).
- If current haemoglobin level is greater than 13.0 g/dl, not depending on the change of haemoglobin in the past 4 weeks, dose should be temporarily withheld until the haemoglobin begins to decrease between 10.5 and 12.0 g/dl, at which point therapy should be reinitiated at 25% reduced from the previous dose (J).

	Current Haemoglobin			
Changes in Hb over past 4 weeks	Hb < 10.5 g/dl)	Hb 10.5 to 12.0 g/dl	Hb 12.1 to 13.0 g/dl	Hb > 13.0 g/dl

Note:

- The iron status should be assessed and need to supplement, if required.
- The dose of the study medication will be rounded off to the highest value. E.g. if subject requires dose of 9000 IU, the dose will be rounded off to 10000 IU because of availability of study medication PFS in multiples of 2000 IU.
- The criteria mentioned about dose adjustment above are recommendation only, Investigator must act for the best interest of the patient whenever necessary

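### Section 5.1.7 rounds doses up to a multiple of 2000 IU with no exception for reductions, so the recommended 25% cut changes nothing at 2000, 4000 and 6000 IU

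*Protocol*

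**What the plan says.** All of the relevant text is in Protocol section 5.1.7.

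- **Aim.** "The dose will be adjusted individually to maintain haemoglobin at a level not exceeding 12 g/dl". The treatment-period text sets a range of 10 to 12 g/dl.
- **Reductions.** Rules C, F and I recommend cutting the last dose by 25% when haemoglobin is 12.1 to 13.0 g/dl. Rule J withholds drug above 13.0 g/dl and restarts, once haemoglobin is back at 10.5 to 12.0 g/dl, at a dose 25% below the previous one.
- **Rounding.** The note after the rules says: "The dose of the study medication will be rounded off to the highest value". Its example is: "if subject requires dose of 9000 IU, the dose will be rounded off to 10000 IU". The reason given is that the prefilled syringes allow only multiples of 2000 IU. Table 1 in section 5.1 lists 2000 and 4000 IU syringes for both products.
- **Fixed step.** For the treatment period the section also says that, when haemoglobin is out of range, "an increase or decrease of 2000 IU per week is allowed for dose adjustment".
- **Discretion.** "The investigator can adjust the dose by their own decision", and the note adds: "The criteria mentioned about dose adjustment above are recommendation only".

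**The concern.** Rounding up works against a reduction. If the rounding step is larger than the cut, the instruction to reduce returns the dose already being given. An investigator who applies rule C, F or I together with the note would then leave a patient whose haemoglobin exceeds the stated 12 g/dl ceiling on an unchanged dose. Under rule J the full previous dose would be restarted after a value above 13.0 g/dl.

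The protocol gives its own reasons to care. Section 1.3 associates high haemoglobin targets with cardiovascular disease, and section 8.9 describes dose-dependent rises in blood pressure and more thrombotic events under epoetin.

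**Working it through.** **Inputs (section 5.1.7; syringe strengths from Table 1).** Rounding unit 2000 IU, direction up. Reduction 25%, so the calculated dose is 0.75 × D for a last dose D. Fixed step 2000 IU per week.

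**Formula.** Dose given = 2000 × ceil(calculated dose / 2000).

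**The plan's own example.** 9000 / 2000 = 4.5, rounded up to 5, and 5 × 2000 = 10000 IU. The example is reproduced.

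**Does the note reach reductions?** Among multiples of 2000 IU, 9000 IU arises from a 25% cut of 12000 (0.75 × 12000 = 9000). As a 25% increase it would need 9000 / 1.25 = 7200 IU, which the syringes cannot supply. Among available doses the example is therefore a reduction that has been rounded up.

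**Applying the cut (D as a weekly total).**

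| Last dose D (IU) | 0.75 × D | Rounded up | Reduction achieved |
|---|---|---|---|
| 2000 | 1500 | 2000 | 0% |
| 4000 | 3000 | 4000 | 0% |
| 6000 | 4500 | 6000 | 0% |
| 8000 | 6000 | 6000 | 25% |
| 10000 | 7500 | 8000 | 20% |
| 12000 | 9000 | 10000 | 16.7% |
| 14000 | 10500 | 12000 | 14.3% |

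**Why exactly three doses.** The cut is lost when 0.75 × D exceeds D − 2000, that is when 0.25 × D < 2000, or D < 8000. The multiples of 2000 below 8000 are 2000, 4000 and 6000. Repeating the cut at a later visit gives the same result.

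**Weekly or per administration.** The text does not say which dose is rounded. The result at 2000, 4000 and 6000 IU is the same either way. Per administration, larger weekly totals are also caught: 3 × 6000 = 18000 IU stays at 18000, whereas weekly rounding gives 0.75 × 18000 = 13500, rounded up to 14000. The weekly reading is therefore the more cautious basis for the claim.

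**Rounding to nearest, ties up.** This also reproduces the 9000 IU example. It would give 4500 → 4000, so 6000 IU would be cut, but 1500 → 2000 and 3000 → 4000 would still leave 2000 and 4000 IU unchanged. The note's wording favours rounding up.

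**Are these doses plausible?** At the stratum limits of 58 and 75 kg in section 9.8, 4000 IU/week is 4000/58 = 69.0 and 4000/75 = 53.3 IU/kg/week. For 6000 IU/week the figures are 6000/58 = 103.4 and 6000/75 = 80.0 IU/kg/week. All lie well inside the 300 IU/kg/week limit.

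**What the fixed step gives.** 4000 − 2000 = 2000 IU and 6000 − 2000 = 4000 IU. It produces a real reduction at the two doses above the smallest syringe.

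**The case against.** The strongest reply is that section 5.1.7 already supplies the remedy. The permitted decrease of 2000 IU per week is exactly one small syringe, so 4000 to 2000 and 6000 to 4000 IU are allowed as the plan stands. The criteria are only recommendations, and the investigator may change the dose at any time. This stands, and it limits the consequence.

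It does not remove the error. The default algorithm still yields no reduction where it instructs one, and no visible sentence says which rule applies. The step is also tied to haemoglobin being out of target range. The range named beside it, under titration, is 10 to 12.5 g/dl, against 10 to 12 g/dl for the treatment period. At 12.1 to 12.5 g/dl an investigator could doubt that the step applies.

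A second reply is that rule J is less alarming than it looks, because restart occurs only at 10.5 to 12.0 g/dl, a band in which rules B, E and H continue the last dose. That is fair, but rule J calls for a lower restart dose, and at these three doses rounding does not deliver one.

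Third, the figure within the treatment-period rules and the body of the dose table are not shown in the text available. Either might state an exception. The arithmetic is certain; the absence of an exception is established only for the written rules and the note.

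**Conclusion.** The point holds as a minor safety-related drafting error. Under the written rules and the note, the recommended 25% reduction is 0% at 2000, 4000 and 6000 IU, on either a weekly or a per-administration reading. It rests on taking the note literally as rounding up.

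Two stronger readings are tempting but unsupported:

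- A reader might infer that patients with haemoglobin above 12 g/dl are held on an unchanged dose, or are certain to be harmed. The fixed step, the advisory status of the criteria, investigator discretion and the withholding above 13.0 g/dl all say otherwise.
- A reader might infer bias in the dose co-primary endpoint, which section 9.4.1 judges against ±45 IU/kg/week. The rule is identical in both arms, and the protocol gives no dose distribution. It supports neither a direction nor a size of effect.

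The share of patients on 6000 IU or less is unknown.

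**What to change.** In section 5.1.7 keep the rounding note and its 9000 IU example, state that the dose is rounded as a weekly total, and add:

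> If rounding up would return a calculated reduction (C, F, I, or restart under J) to the previous weekly dose, lower the weekly dose by 2000 IU, as section 5.1.7 already allows; at 2000 IU per week, withhold until Hb is 12.0 g/dl or below, then resume.

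Result: 4000 becomes 2000 IU and 6000 becomes 4000 IU per week. From 8000 IU per week upward the rounded reductions are those in the table above. Withholding at 2000 IU is needed because no smaller syringe exists and a patient on that weekly total is already dosed once a week. The fixed step and investigator discretion stay as written.

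**Cost.** Two sentences, with no new data, visits or syringe strengths. The cuts become 2000/4000 = 50% and 2000/6000 = 33% instead of 25%, so haemoglobin must be watched for a fall below target. Stating the weekly basis also settles how larger split doses are rounded. Increases are still rounded up as now.
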